#### Enrollment Criteria:

##### *Inclusion criteria*

1. Existing ventriculoperitoneal CSF shunt on which the patient is dependent
2. At least one symptom of shunt malfunction as determined by the investigator, such as but not limited to seizure, fever, headache, vision problems, dizziness, disorientation, confusion, vomiting, lethargy, irritability, difficulty waking or staying awake, swelling along shunt tract, enlargement of head, loss of balance, gait disturbance, and loss of sensory or motor function

3. Suspicion of shunt obstruction warrants the performance of a test for this condition in the investigator's judgement
4. Region of intact skin overlying an unambiguously identifiable chronically indwelling ventricular shunt which crosses the clavicle and is appropriate in size for application of the study device
5. Available for follow-up for up to seven days
6. Signed informed consent by patient or a parent, legal guardian, health care agent, or surrogate decision maker (according to local statutes, and collectively referred to as "surrogates" in this protocol)

*Exclusion criteria*

1. Presence of multiple shunts, or presence of more than one distal shunt catheter (regardless of function) crossing the clavicle ipsilateral to the shunt with suspected obstruction
2. Use of the study device would interfere with standard patient care, or emergency surgery that cannot be delayed
3. Presence of an interfering open wound or edema over any portion of the shunt
4. Patient-reported history of adverse skin reactions to adhesives
5. Investigator judges that the subject is likely to be lost to follow-up due to unavailability or clinical outcome being unobtainable
6. Participation in the study will interfere with, or be detrimental to, administration of optimal health-care to the subject
7. Prior enrollment in this study (multiple main study enrollments of the same patient are disallowed)
8. Participation in any other investigational procedural, pharmaceutical, and/or device study that may influence the collection of valid data under this study

#### Study Device:

Device name: FlowSense®

Device description: FlowSense (Rhaeos, Inc.; Model Number FS01), the study device, is designed to provide non-invasive wireless measurement of flow in implanted CSF shunts via thermal anisotropy measurements. The single-use device, which includes a low-power heating element, a set of temperature sensors, a Bluetooth low energy (BLE) wireless chip, and a coin cell battery enclosed in a flexible housing, is similar in size to a conventional adhesive bandage and communicates with an iPad application to perform measurements and report the results.

#### Research Questions(s)/Hypothesis(es):

Primary objectives: The primary objectives of this study are to determine the sensitivity and specificity of the study device for identifying the presence or absence of complete shunt failure in symptomatic hydrocephalus patients with CSF shunts.

Secondary objectives: The secondary objectives of this study are to determine the accuracy, positive predictive value (PPV), and negative predictive value (NPV) of the study device in this population. Additional objectives include collecting and describing clinical, demographic, and hydrocephalus (e.g., etiology, shunt system type, shunt system brand, shunt valve settings) characteristics of the study population, device user feedback, and shunt testing data (e.g., imaging studies). Additional study device diagnostic and performance data (e.g., temperature data and error codes) will be collected for adjudication and review purposes. The diagnostic performance of an additional flow

assessment algorithm will also be assessed using the data acquired in this study by the study device.

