#### Study Design:

This is a prospective, open-label, blinded, multi-center, single-arm observational study of up to 150 (roll-in and main study) subjects at up to 10 trial sites. Patients with an existing CSF shunt and symptoms of a shunt failure will be recruited by the clinical investigators based on the inclusion and exclusion criteria.

Subjects will undergo evaluation with the FlowSense device and standard-of-care testing and will be followed for 7 days to determine if a revision was performed to repair or replace the existing shunt. In subjects undergoing a revision, intraoperative assessment of shunt functionality will establish the presence or absence of a complete shunt obstruction. FlowSense device data will be used to categorize shunt function as “flow confirmed” or “flow not confirmed.” This trial will evaluate the ability of the study device to accurately distinguish between functioning (flowing) and non-functioning (non-flowing) shunts.

Clinical staff will be required to complete training on the protocol and device measurement procedures as well as complete a roll-in study device measurement prior to enrolling main study patients.

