#### Statistical Procedures:

The co-primary endpoints for this study are sensitivity and specificity. Performance measures (sensitivity, specificity, accuracy, positive predictive value (PPV), and negative predictive value (NPV)) will be estimated along with 95% two-sided confidence intervals (CI).

To calculate the performance measures, the study device output of either “flow confirmed” or “flow not confirmed” and the standard-of-care clinical treatment will place each patient into one of the following categories:

True Positive (TP): Device outputs “flow not confirmed” AND a shunt revision surgery with confirmed shunt failure is performed

False Positive (FP): Device outputs “flow not confirmed” AND either no shunt revision surgery is performed for 7 days or a shunt revision surgery without a confirmed shunt failure is performed

True Negative (TN): Device outputs “flow confirmed” AND either no shunt revision surgery is performed for 7 days or a shunt revision surgery without a confirmed shunt failure is performed

False Negative (FN): Device outputs “flow confirmed” AND a shunt revision surgery with confirmed shunt failure is performed

If a patient does not fall within one of these categories (e.g., if shunt patency was not assessed during revision surgery), data for that patient will not be included in the endpoint calculation. Study device sensitivity will be calculated as  $TP / (TP + FN)$  and study device specificity will be calculated as  $TN / (TN + FP)$ .

A minimum of 30 “positive” patients (those who undergo shunt revision surgery with a confirmed shunt failure) will be enrolled.

Secondary subgroup analyses will be performed to report on any variation between pediatric and adult patients. Additional subgroup analyses will be performed to identify any patient characteristics that may impact device performance.

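### PPV and NPV taken from the enrolled 2x2 table hold for the enrolled mix of patients and may not carry over to symptomatic shunted patients in general; the plan should add them over a stated range of failure prevalence

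*Combined protocol and SAP*

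**What the plan says.** The primary objectives (Research Questions/Hypotheses) concern "identifying the presence or absence of complete shunt failure in symptomatic hydrocephalus patients with CSF shunts". The secondary objectives follow directly: to "determine the accuracy, positive predictive value (PPV), and negative predictive value (NPV) of the study device in this population". The most natural referent of the last phrase is the symptomatic shunted population just named.

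Statistical Procedures puts each patient in one of four cells (TP, FP, TN, FN) by device output and by revision with or without confirmed failure. Accuracy, PPV and NPV, like the co-primary measures, "will be estimated along with 95% two-sided confidence intervals (CI"). Formulas are printed only for sensitivity and specificity, but PPV and NPV follow from the same four cells. No failure prevalence is assumed and no standardisation is described. Patients who fit no cell, for example because patency was not assessed at revision, are left out.

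Four features bear on who ends up in the table:

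- Study Design: patients "will be recruited by the clinical investigators based on the inclusion and exclusion criteria".
- Enrollment Criteria, exclusion 2: "Use of the study device would interfere with standard patient care, or emergency surgery that cannot be delayed". Inclusion 3 and exclusions 5 and 6 also rest wholly or partly on judgement at the site.
- Statistical Procedures: "A minimum of 30 “positive” patients", with no rule for how they are to be found.
- Study Design: a "single-arm observational study of up to 150 (roll-in and main study) subjects at up to 10 trial sites".

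**The concern.** PPV and NPV depend directly on the share of patients who truly have a failed shunt. A device with unchanged sensitivity and specificity gives a different PPV and NPV when that share changes. The planned 95% intervals describe sampling error around the enrolled share. They say nothing about how far that share lies from the one in symptomatic shunted patients at large.

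Several features could move the enrolled share. Exclusion 2 plausibly removes a group rich in true failures, which would lower it. The need to find 30 positives under a cap could raise it, if sites came to favour patients who look likely to be revised. Investigator judgement and the dropping of unclassifiable patients could act either way. A reader who takes the reported PPV or NPV as the figure for any symptomatic shunted patient would be carrying over a prevalence that the report had not examined.

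**Working it through.** **Inputs.** From the documents: at least 30 positives and at most 150 subjects including roll-in. Assumed, because the documents give none: sensitivity (Se) 90%, specificity (Sp) 80% and prevalence p from 10% to 50%. The documents give no derivation of the 30, so there is no planned calculation to reproduce.

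**Step 1: dependence on prevalence.**

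- PPV = Se·p / [Se·p + (1 − Sp)(1 − p)]
- NPV = Sp(1 − p) / [Sp(1 − p) + (1 − Se)p]
- Accuracy = Se·p + Sp(1 − p)

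| p | PPV | NPV | Accuracy |
|---|---|---|---|
| 10% | 0.09/(0.09+0.18) = 33% | 0.72/(0.72+0.01) = 98.6% | 81% |
| 20% | 0.18/(0.18+0.16) = 53% | 0.64/(0.64+0.02) = 97.0% | 82% |
| 30% | 0.27/(0.27+0.14) = 66% | 0.56/(0.56+0.03) = 94.9% | 83% |
| 50% | 0.45/(0.45+0.10) = 82% | 0.40/(0.40+0.05) = 88.9% | 85% |

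Accuracy does not move at all when Se = Sp. At Se 90%, Sp 70% it goes from 72% at p = 10% to 78% at p = 40%.

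**Step 2: do the planned intervals cover this?** Take 30 positives and 120 negatives, treating all 150 places as main-study places for illustration. The expected table is TP 27, FN 3, TN 96, FP 24.

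- PPV = 27/51 = 53%, exact 95% interval 38% to 67%.
- NPV = 96/99 = 97%, exact 95% interval 91% to 99%.

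The PPV at p = 10% (33%) and at p = 50% (82%) both lie outside the first interval. The NPV at p = 50% (88.9%) lies outside the second; the NPV at p = 10% (98.6%) lies inside.

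**Step 3: the floor as a stopping rule only.** If recruitment ran without selection and stopped at the 30th positive, the expected observed share would be 20.5% for a true 20% and 30.7% for a true 30% (simulation). Over true prevalences of 15% to 30%, with Se = Sp = 80% or Se 90% and Sp 70%, mean PPV rises by about 0.8 percentage points, NPV falls by 0.1 to 0.3 points and accuracy changes by about 0.1 point. That is negligible.

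**Step 4: the floor together with the cap.** Meeting both requires a share of at least 30/150 = 20%, or 30/140 = 21.4% if 10 places go to roll-in (an assumption). With 140 main-study patients and no selection, the binomial probability of at least 30 positives is 0.03 at p = 15%, 0.37 at 20%, 0.86 at 25% and 0.99 at 30%. So the floor presses on selection only if true prevalence is near or below 20%.

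**Step 5: the emergency exclusion.** If it removes a share e of positives, enrolled prevalence is q = p(1 − e)/[p(1 − e) + 1 − p]. At p = 30% and with the Se and Sp of Step 1:

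- e = 10%: q = 0.27/0.97 = 27.8%. PPV goes from 65.9% to 63.4% and NPV from 94.9% to 95.4%.
- e = 30%: q = 0.21/0.91 = 23.1%. PPV goes to 57.4% and NPV to 96.4%.

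The values of e are assumptions. The shift is modest and opposite to the one that pressure from the floor would cause.

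**The case against.** The strongest reply is that nothing is wrong with the estimates. Patients enter one prospective cohort on symptoms and eligibility, and failed and working shunts are not sampled separately. PPV and NPV are directly estimable in such a cohort. If the population is read as patients meeting the Enrollment Criteria, the objective is met. Exclusion 2 also partly defines who could be tested at all, since a patient whose surgery cannot be delayed cannot wait for a measurement. Finally, once sensitivity and specificity are reported, any reader can compute PPV and NPV at a chosen prevalence.

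Most of this stands, and it rules out three stronger readings that a reader might infer.

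- *The secondary objective goes unanswered.* It does not. The values are valid for the enrolled, classifiable patients; the limit is on carrying them further.
- *Enrolment is not consecutive, or the sample is enriched.* The documents neither require nor rule out consecutive enrolment. The floor is a minimum count with no quota or rule favouring likely positives, and Step 3 shows that by itself it hardly matters.
- *The 10% to 50% table measures the bias.* It shows how sensitive PPV and NPV are to prevalence. It is not an estimate of the shift that these features cause.

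The reply does not remove the gap between the population named in the objectives and the patients counted in the table. Nor does it supply intervals for the values that a reader would compute at another prevalence.

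**Conclusion.** The concern holds as a limit on generalisation of two secondary measures. Raw PPV and NPV describe the enrolled, classifiable patients, and the plan gives no means of carrying them to symptomatic shunted patients with a different failure prevalence. The potential size is large for PPV (33% to 82%) and moderate for NPV (98.6% to 88.9%) over prevalences of 10% to 50%, under assumed sensitivity 90% and specificity 80%. How far enrolled prevalence actually departs from that of the wider population, and in which direction, cannot be told from the documents. Accuracy is little affected, and the co-primary sensitivity and specificity do not depend on prevalence in this direct way.

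**What to change.** In the secondary analysis:

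1. Report the observed prevalence of confirmed failure beside PPV and NPV, and label the raw values as specific to the enrolled sample.
2. Add PPV and NPV computed from the estimated sensitivity and specificity over a pre-stated prevalence range, for example 10% to 50%, with 95% intervals. One simple route uses likelihood ratios: odds of PPV = [p/(1 − p)]·LR+ with LR+ = Se/(1 − Sp), and NPV = 1/{1 + [p/(1 − p)]·LR−} with LR− = (1 − Se)/Sp. Log-scale intervals for LR+ and LR− carry straight through. For the table in Step 2, LR+ = 0.9/0.2 = 4.5 and the standard error of its log is √(1/27 − 1/30 + 1/24 − 1/120) = 0.192, so the interval is 3.09 to 6.56. At p = 10% the prior odds are 1/9, which gives PPV 33% (26% to 42%).
3. State the assumption behind this table: sensitivity and specificity do not change with case mix. If selection also alters the spectrum of patients, the table does not correct for that.

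The cost is one table with no new patient data. The downside is that headline PPV and NPV become a range that may look less favourable than a single figure. A count of exclusion 2 cases in the screening records would help interpretation but is optional.

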#### Scientific Abstract:

Diagnosing cerebrospinal fluid (CSF) shunt failure can be difficult and currently relies on a combination of indirect and/or invasive methods. This study will evaluate the performance of the non-invasive FlowSense wireless device to rapidly assess shunt flow.

The objective of this study is to establish performance of the study device in subjects presenting with symptoms of a possible shunt failure.

This is a prospective, blinded, observational multi-center study. Patients will undergo evaluation with the FlowSense device and standard-of-care imaging and will be followed for 7 days to determine if a revision was performed to repair or replace the existing shunt. In patients undergoing a revision, intraoperative assessment of shunt functionality established the presence or absence of a complete obstruction. FlowSense device data will be used to categorize shunt function as “flow confirmed” or “flow not confirmed.”

#### Lay Abstract:

Cerebrospinal fluid (CSF) shunts often fail. However, it can be difficult to know when the device has failed because the symptoms patients experience are common (such as headache, nausea, and tiredness) and can have many causes that are unrelated to the CSF shunt. In addition, the current tests used to determine if a CSF shunt has failed are not always correct. When a CSF shunt does fail, patients typically have a shunt revision surgery. During the surgery, the entire shunt or some of its components are repaired or replaced.

This trial will determine if the study device can accurately distinguish between functioning (flowing) and non-functioning (non-flowing) shunts. The study will enroll patients who have a CSF shunt and are experiencing symptoms of possible shunt failure. The patients and clinical staff will not see the study device results, and the patients will receive their normal care. The patients will be followed for 7 days to see if they have a shunt revision surgery. In patients who do have surgery, the doctors will check the shunt to see if fluid can flow through it. The study device results of “flow confirmed” or “flow not confirmed” will then be compared to the patient outcome (no revision surgery/revision surgery with a flowing shunt or revision surgery with a non-flowing shunt).
